8.6 Withdrawal Criteria – Individual Participants

An intention-to-treat approach will be used in these analyses. Participants will not be replaced. All data acquired prior to termination for the reasons outlined below will be included in the primary analysis unless a participant withdraws consent for the use of those data. Every effort will be made to conduct a final study visit with the participant, and participants will be followed clinically until, if applicable, all potentially study-related adverse events resolve.

- Withdrawal of consent by the participant
- Withdrawal of the participant by the investigator
- Intercurrent illness or event that precludes further visits to the study site or ability to evaluate disease.

9 ETHICAL CONSIDERATIONS AND COMPLIANCE WITH GOOD CLINICAL PRACTICE

9.1 Statement of Compliance

This study will be conducted in compliance with the protocol and consistent with current Good Clinical Practices (GCP), adopting the principles of the Declaration of Helsinki, and all applicable regulatory requirements (*ICH E6, 45CFR46, and FDA 21CFR sections 11, 50, 56, 312*).

The study protocol, along with the required informed consent forms, will be approved by a Central Institutional Review Board (CIRB), and/or each participating institution's Institutional Review Board (IRB) or Ethics Committee/Research Ethics Board (EC/REB) at international sites prior to the initiation of any research procedures (at the site). Any amendments to the protocol or consent materials must also be approved before they are implemented.

In addition to details described in the sections above (informed consent, confidentiality, and risks and benefits), the investigators have reviewed and considered ethical ramifications in the design and development of this protocol. The investigators have made every effort to minimize and monitor risks and discomforts to participants throughout the course of the study.

9.2 Participating Centers

Participating TrialNet clinical sites must have an appropriate assurance, such as a Federal-wide Assurance (FWA) or an Unaffiliated Investigators Agreement (UIA), with the Office for Human Research Protections (OHRP), since they are actively engaged in research and provide informed consent. The protocol and consent forms will be approved by a Central Institutional Review Boards (CIRB) or Institutional Review Boards or Ethics Committees/Research Ethics Boards at each of the participating clinical sites. HIPAA and applicable local regulations will be followed by each participating institution in accordance with each institution's requirements. The participating international sites will obtain approval from their corresponding review boards in accordance with their local procedures and institutional requirements.

The investigator is required to keep accurate records to ensure the conduct of the study is fully documented. The investigator is required to ensure that all case report forms are legibly completed for every participant entered in the trial.

The investigational sites participating in this study will maintain the highest degree of confidentiality permitted for the clinical and research information obtained from participants participating in this study. When a participant participates in this study at more than one TrialNet site, sharing of this information is required. Sharing of information obtained during this study between TrialNet clinical centers, affiliates, TrialNet Hub and TNCC will be done to assure participant understanding and consent, safety, and adherence to protocol. Medical and research records will be maintained at each site in the strictest confidence. However, as a part of the quality assurance and legal responsibilities of an investigation, the investigational site must permit authorized representatives of the sponsor(s) and regulatory agencies to examine (and when required by applicable law, to copy) records for the purposes of quality assurance reviews, audits and evaluation of the study safety and progress. Unless required by the laws permitting copying of records, only the coded

identity associated with documents or other participant data may be copied (obscuring any personally identifying information). Authorized representatives, as noted above, are bound to maintain the strict confidentiality of medical and research information that may be linked to identify individuals. The investigational site will normally be notified in advance of auditing visits.

9.3 Informed Consent

The process of assuring that individuals (and parent/guardian if less than 18 years of age) are making an informed decision about participating in this study includes both verbal and written communication. Written materials include a Volunteer Handbook, Volunteer Understanding Assessment, and written consent forms. There is one main consent form for this study that includes screening, intervention and follow-up phases of the study that describes the procedures, risks, and benefits, and eligibility. A second consent form (Follow-up Form) is for use at clinical sites that will be performing the post-treatment visits, but not the treatment visits. The consent forms will be reviewed with participants (and their parent/guardian in the case of participants under 18 years of age) and the participant will be given time to review the written consent form and ask questions. An assent form has also been developed for participants less than 18 years of age (unless local IRB/REB requirements differ in procedure).

As part of the informed consent process, the participant and/or parent or guardian (if the participant is less than 18 years of age) will also be required to complete a short, written Volunteer Understanding Assessment that is designed to ensure that the participant understands the study, as well as what is being asked of him/her. The participant will be given a copy of their consent/assent forms.

The consent process will be conducted by qualified study personnel (the Trial Investigator or Study Coordinator and/or as described in the delegation log). All participants (or their legally acceptable representative) must read, sign and date a consent form prior to participation in the study, and/or undergoing any study-specific procedures.

The informed consent form must be updated or revised whenever there is new, clinically significant information applicable to the safety of the participants, when indicated for a protocol amendment, and/or whenever any new information becomes available that may affect a participant's participation in the study.

Participants will be re-consented if they reach the age of 18 years while enrolled in the study.

9.4 Study Participant Confidentiality

Study participant data, which is for reporting purposes, will be stored at the TrialNet Coordinating Center. Data sent to the Coordinating Center will identify participants by the unique TrialNet Identification Number. The data entry system at the Coordinating Center is a secured, password protected computer system. At the end of the study, all study databases will be archived at the Coordinating Center for long-term storage.

Stored samples including genetic samples could be utilized to learn more about causes of type 1 diabetes, its complications (such as eye, nerve, and kidney damage) and other conditions for which individuals with diabetes are at increased risk, and how to improve treatment. The results of these future analyses, and any mechanistic studies will not be made known to the participant.

9.5 Risks and Benefits

The risks of this study are presented in this protocol, and informed consent form. There is no guaranteed benefit to participants for their participation in the study.

Special consideration regarding risks and benefits for children is described in section 6.1.

10 STUDY ADMINISTRATION

10.1 Organizational Structure

This study is part of Type 1 Diabetes TrialNet, which is funded by the National Institutes of Health. Funding will cover the costs of administration and laboratory tests associated with this study.

10.2 Role of Industry

Sanofi will be providing the active agent, ATG for the study.

10.3 Groups and Committees

10.3.1 ATG Study Chair Committee

The Study Chair and TrialNet Executive Committee will receive periodic reports from the TNCC on the progress of the study. These will include accrual rates and baseline demographic characteristics. Interim data summaries provided to others (except those that could lead to unmasking of study outcome) will first be supplied to the Study Chair for review. Criteria and results of ongoing monitoring of the TrialNet labs in terms of reproducibility will also be provided on a routine basis and reported on during TN28 ATG Study Chair Committee meetings, as scheduled. As appropriate, abstracts and manuscripts dealing with the progress of the trial shall be directed by the TN28 ATG Study Chair Committee.

10.3.2 TrialNet Chairman's Office and TNCC

The TrialNet Chairman's Office, TrialNet Hub and TNCC will work together in providing leadership to the TrialNet study group to include protocol and manual preparation, training for clinical sites, development of statistical design for each study, and analysis of study results. The TNCC will also coordinate interactions among the participating TrialNet Clinical Centers, test laboratories including TrialNet Core Laboratories and other subcontract laboratories, NIDDK, and other sponsoring agencies.

10.3.3 Clinical Sites

Principal Investigators at each participating TrialNet clinical site will oversee all operations at that site. The clinical sites will forward all laboratory and data collection form information to the TNCC for analysis. Direct communication and site visits, as needed, will facilitate evaluation of the trial management.

10.3.4 Clinical Site Monitoring

In order to conduct this study with established research principles, site visits will be conducted during the study to evaluate study conduct and ensure participant safety. All sites will be monitored by the TNCC and appropriate TrialNet committees for patient enrollment, compliance with protocol procedures, completeness and accuracy of data entry, the occurrence and reporting of adverse

events (Aes) and serious adverse events (SAEs), site pharmacy accountability/operations and to confirm the presence of appropriate IRB/REB regulatory approvals/documents.

10.3.5 Medical Monitor and Data Safety and Monitoring Board (DSMB)

All adverse events will be recorded on the adverse event forms, which will be sent to the local IRBs/REBs, per their reporting requirements, and to the Coordinating Center.

An independent physician will be designated to serve as the medical monitor for this study who will maintain regular contact with the study and the Study Chair. The medical monitor will review all adverse event reports, masked to treatment assignment, and will file event reports with regulatory authorities as appropriate.

The DSMB will meet approximately every 3 months following randomization of the first participant and as needed to review indicators of safety. In addition, they will meet every 6 months to review the interim effectiveness and potential toxicity of the study treatments based on interim analyses of indicators of effectiveness and safety prepared by the TNCC separately by treatment group. The DSMB will independently evaluate whether there are grounds to modify or discontinue the study.

10.4 Sample and Data Storage

Samples to be stored for research purposes will be located at the NIDDK Repository and at TrialNet Laboratories. While TrialNet is active, the use of the samples will be restricted to TrialNet researchers unless researchers from outside of TrialNet obtain approval from TrialNet and the NIDDK to utilize the samples. All samples will be coded with unique study numbers, but TrialNet researchers will be able to identify samples if it is necessary to contact participants for reasons of health or for notification to them about future studies. Approval from TrialNet would be required before such linkage could occur. Researchers from outside of TrialNet will not be permitted to identify samples.

Data collected for this study will be sent to the TNCC. De-identified data will be stored at the NIDDK Repository, under the supervision of the NIDDK/NIH, for use by researchers including those outside of TrialNet.

With permission of the participant, when TrialNet is completed, samples will continue to be stored at the NIDDK Repository. Since the stored data will be fully de-identified upon the completion of TrialNet, it will no longer be possible to identify samples. Thus, whereas a sample can be destroyed upon a participant's request during the existence of the TrialNet, it can no longer be destroyed once TrialNet is completed. However, there will still be the potential to link data derived from the samples with data that had been derived from TrialNet studies. Once TrialNet is completed, researchers will only obtain access to samples through grant proposals approved by the NIDDK. The NIDDK will convene an external panel of experts to review requests for access to samples.

10.5 Preservation of the Integrity of the Study

The scientific integrity of the trial dictates that results be reported on a study-wide basis; thus, an individual Center will not report the data collected from its site alone. All presentations and publications using TrialNet trial data must protect the main objectives of the study. Data that could be perceived as threatening the study outcome will not be presented prior to release of the primary study outcomes. Approval as to the timing of presentations of data and the meetings at which they might be presented will be granted by the TrialNet Steering Committee. Study results should be discussed with the news media only upon authorization of the Steering Committee, and never before the results are presented. Any written statements about this study that are shared with national media must be approved by TrialNet before release.

10.6 Participant Reimbursement and Compensation

Participants may be compensated for each visit attended in the study. In compliance with ICH Guidance E6, the amount and method of payments to participants shall be designed to avoid coercion or undue influence on the study participants. Payments to participants will be prorated and not wholly contingent on completion of the trial by the participant.

APPENDIX 1 – Schedule of Assessments

Week of Trial						1	2											
Month of Trial								3	6	12	18	24	30	36	42	48	54	60 ¹⁶
Day of Trial		0	1	2	4	7												
Visit number	-1	0	1	1.1	1.2	1.3	2	3	4	5	6	7	8	9	10	11	12	13
Visit Window		≤ 52 days stage 2 criteria + 1 or more high risk markers	≥ 12 hrs to ≤ 30 hrs from start dose 1			+/- 1 day	+/- 3 days	+/- 7 days	+/- 14 days									
Informed Consent	X																	
Randomization		X																
ATG/Placebo Infusion 1 and 2		X	X															
Medical History	X	X																
Adverse Events Assessment		X	X	X	X	X	X	X	X	X	X	X	X	X	X	X	X	X
Concomitant Medication	X	X	X	X	X	X	X	X	X	X	X	X	X	X	X	X	X	X
Physical Exam ¹	X	X	X				X	X	X	X	X	X	X	X	X	X	X	X
Vital Signs	X	X	X				X	X	X	X	X	X	X	X	X	X	X	X
Urine Pregnancy Test	X	X					X	X	X	X	X	X	X	X	X	X	X	X
TB Test (IGRA) (local)	X																	
CD4/CD8 Panel ² (local)	X	X	X				X	X	X	X								
CBC with Differential ³ (local)	X	X	X				X	X	X	X	X	X	X	X	X	X	X	X
Chemistries and liver function tests	X	X	X				X	X	X	X	X	X		X		X		X
PT/PTT/INR (local)		X	X															
EBV/CMV viral load and serology ⁴	X									X								
HIV, Hepatitis B and C serology	X																	
COVID Test ⁵ (local)		X																
Random Glucose (local) ⁶		X																
OGTT ⁷	(X) ⁸							X	X	X	X	X	X	X	X	X	X	X
HbA1c	(X) ⁸							X	X	X	X	X	X	X	X	X	X	X
Autoantibodies	(X) ⁸																	
ATG Levels ⁹		X	X	X	X	X	X	X										
ATG Drug Induced Antibodies (DIA) ¹⁰		X			X	X	X	X										
Mechanistic Assessments ¹¹		X	X				X	X	X	X	X	X	X	X	X	X	X	X
Interim Contact ¹²		X			X		X	X	X	X	X	X	X	X	X	X	X	X

Week of Trial						1	2											
Month of Trial								3	6	12	18	24	30	36	42	48	54	60 ¹⁶
Day of Trial		0	1	2	4	7												
Visit number	-1	0	1	1.1	1.2	1.3	2	3	4	5	6	7	8	9	10	11	12	13
Visit Window		≤ 52 days stage 2 criteria + 1 or more high risk markers	≥ 12 hrs to ≤ 30 hrs from start dose 1			+/- 1 day	+/- 3 days	+/- 7 days	+/- 14 days									
Flu Vaccination ¹³																		
CGM Blinded Wear ¹⁴	X							X	X	X	X	X	X	X	X	X	X	X
Fecal Sample ¹⁵		X						X		X								

- Complete physical examination at screening and annually thereafter. Interim medical history and directed/limited physical examination every visit. Tanner Staging to occur at screening or baseline visit and annually thereafter. Once Tanner Stage assessed as ≥ 3 , no further genitalia examination required. Directed exam as indicated by symptoms.
- CD4/CD8 panel will continue to be monitored until the CD4 count is above 500. CD4/CD8 ratio can be collected at screening visit or baseline (Visit 0).
- CBC to be obtained prior to the first infusion, immediately following the first infusion, prior to the second infusion and obtained after the completion of the second infusion.
- Viral PCR/Serology: All participants will have serology and PCR for EBV and CMV at screening. CMV and/or EBV seronegative participants must be PCR negative, CMV seropositive participants must be CMV PCR negative, and EBV seropositive participants must have EBV PCR <2000 IU/mL within 30 days of randomization. All participants may not have had signs or symptoms of an EBV or CMV compatible illness lasting longer than 7 days within 30 days of randomization. Additional EBV and/or CMV PCR testing may be obtained locally if necessary clinically. Subsequent EBV and/or CMV PCR/Serology will only be performed for symptomatic participants as clinically indicated. At Month 12, EBV/CMV serology will be processed real-time and PCR for EBV/CMV will be stored unless clinically indicated.
- Covid-19 test to be done within 7 days of the first dose (infusion 1) to ensure no active infection is present before treatment administration. Additional Covid-19 testing will be performed at specified visits based on exposure, symptoms and investigator's recommendation.
- Random glucose to be obtained prior to randomization to monitor progression to Stage 3 T1D. If value is less than 200, randomization can proceed. If value is above 200, a safety check must be done by the study physician for Stage 3 T1D.
- If OGTT consistent with DM, repeat as soon as possible but no less than one day apart. Aim to repeat within 1 month. Mechanistic samples, including CBC/differential will be collected at the confirmatory OGTT visit.
- If not done as part of the TrialNet Pathway to Prevention study or other TrialNet Prevention study, OGTT, HbA1c and Islet Autoantibodies may be done at the screening visit.
- ATG Levels (PK): Samples will be drawn on 12 participants in each of the following age groups: <18 years and ≥ 18 years at randomization. Day 0 samples to be drawn before infusion 1 and 6 hours after the completion of infusion 1. Day 1 samples to be drawn before infusion 2. Additional samples will be collected on Days 2, 4, and 7, Week 2, and Month 3.
- ATG Drug Induced Antibodies (DIA): Samples will be drawn on 12 participants in each of the following age groups: <18 years and ≥ 18 years at randomization. Pre-infusion sample will be drawn on Day 0. Samples will also be drawn on Days 4 and 7, Week 2, and Month 3.
- May include samples for RNA, plasma, serum, DNA, measures of B and T cell number and function to understand the effect of therapy on the immune system and infectious disease. The following HLA typing will also be performed: Class I (HLA-A, B, C) and Class II (DRB, DBA, DQB). The schedule for these assessments may vary as appropriate. At no time will the blood draw volume exceed what is allowable according to the participant's age and body weight (for participants <18 years, 5 mL/kg per visit, 9.5 mL/kg in an 8-week period).
- Contact with participant every other day will occur once the study treatment is complete until the 2-week visits. Following the 2-week visit weekly contact with participant will occur until the 3-month visit. Contact thereafter will occur every 3 months, in-between in person study visits to assess for symptoms of diabetes and changes in health. Participants who report signs/symptoms consistent with Stage 3 T1D will be asked to complete a PRN OGTT study visit. At any time point in between study visits, participants experiencing symptoms of diabetes are to contact their clinical trial contact(s). Covid-19 assessments may be completed PRN through the end of the study based on exposure and symptoms.
- Participants are required to receive killed influenza vaccination at least 2 weeks prior to randomization when vaccine for the current or upcoming flu season is available.
- Frequency of CGM blinded, 7-10 day wear will occur at the screening visit, 3 month visit and then semi-annually per schedule of visits.
- Fecal sample: Willing participants will collect fecal samples within +/-3 days of the indicated visit at home and either bring to the research visit or ship samples back to the site. Participants who agree to collect samples should be encouraged to provide samples at all 3 timepoints.
- The bi-annual schedule will continue until the primary endpoint of the study occurs. After the primary endpoint is met, all participants will be followed for an additional year. Participants who develop Stage 3 T1D at any point during the year post-primary endpoint, will be followed for 1 year following their diagnosis.

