4 PARTICIPANT MANAGEMENT

4.1 Overview

Eligible participants will receive either low-dose ATG or placebo. Infusion will be given as follows:

- Infusion 1 (visit 0) will be ATG/Placebo at 0.5 mg/kg IV over a minimum of 6 hours.
- Infusion 2 (visit 1) will be ATG/Placebo at 2 mg/kg IV over a minimum of 6 hours.

Participants will undergo screening visits to determine eligibility. Eligible participants will be randomized to one of two treatment groups (ATG or Placebo) as long they qualified for trial enrollment based on sections 3.1.1 and 3.1.2 for eligibility criteria. Study drug will be administered either in hospital (inpatient unit) or in outpatient infusion centers (criteria for outpatient defined later in this section) at the investigator's and institution's policy. Individuals will receive oral and IV premedication and the first dose of ATG/placebo will be administered over a minimum of 6 hours (maximum of 10 hours).

A CBC will be drawn prior to the first infusion and immediately after the completion of the first infusion. CBC will also be drawn prior to the 2nd infusion and the dose will remain at 2mg/kg, independent of the CBC results. The platelet count between the first 1st CBC and the CBC drawn prior to the second infusion will be reviewed to monitor for side effects of heparin-induce thrombocytopenia (criteria listed in section 4.5.2).

Participants will also have PT/INR/aPTT drawn prior to the first infusion and second infusion. Participants will also be asked about symptoms related to bleeding, bruising and nosebleeds prior to the start of the second infusion. A directed physical exam will be completed and vital signs will be collected from participant prior to the administration of infusion 2.

The second dose of ATG/placebo will be administered no less than 12 hours and no later than 30 hours from the start of the first infusion. The second dose of ATG/placebo will be given over a minimum of 6 hours (maximum of 10 hours).

Should a participant receive study agent as an outpatient (defined as leaving the medical facility in between administration of infusion 1 and infusion 2), the following criteria need to be met to allow for discharge from the facility:

- Resolution of any grade 2 adverse events the participant experienced during the infusion with or without medical intervention
- Clinically stable with normal mentation for at least 2 hours
- Stable vital signs without fever, hypotension or tachycardia for at least 2 hours

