4.5 Premedication

To reduce the risk of adverse reactions to ATG infusion for those assigned to active treatment, methylprednisolone 0.25 mg/kg IV will be given no less than 30 minutes before each infusion of active drug. Participants assigned to the placebo group will be given a placebo (saline) infusion similar in appearance no less than 30 minutes before each infusion.

Both groups: Participants in both groups will be pre-medicated with an antihistamine and acetaminophen PO at least 30 minutes before each infusion and every 4–6 hours as needed during the infusion, as follows:

- Diphenhydramine 1.25 mg/kg/dose to a maximum of 50 mg. (*Comparable antihistamine may be used in countries who do not have diphenhydramine available*).
- Acetaminophen 10–15 mg/kg/dose to a maximum of 650 mg.

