5.3 Mechanistic Outcome Assessments

TrialNet will perform immune and genetic assays to further understand mechanisms that may be underlying the type 1 diabetes disease process and response to therapy. TrialNet proposes to evaluate the relationships between changes in immune cells and the delay in onset of T1D. Transcriptomic and serologic studies are planned. In addition, the relationship between specific genotypes and the responses to ATG may be explored. For these purposes, samples for PMBC, DNA, RNA, plasma, and serum may be obtained. The following HLA typing will also be performed: Class I (HLA-A, B, and C) and Class II (DRB, DQA, DQB).

Fecal samples will also be collected from willing participants to explore whether the gut microbiome can predict response to therapy and whether therapy induces changes in the microbiome.

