5.5 Visit Windows

Randomization and the baseline visit must occur within 7 weeks (52 days) of having met two or more of the high-risk markers. All subsequent treatment visits and follow up visits in Appendix 1 must occur within the time limits specified below:

Visit Windows	
Visit -1:	Open window for screening for any participants with 2+ Antibodies
Visit 0:	Randomization within 7 weeks (52 days) of having met ADA Stage 2 criteria and at least one of the high-risk markers. First dose of ATG/placebo given over minimum of 6 hours and maximum of 10 hours. The infusion can be slowed or temporarily stopped to treat signs or symptoms of cytokine release with a maximum infusion time for each infusion of 10 hours.
Visit 1:	The second dose should be given no earlier than 12 hours and no later than 30 hours from the start of the first infusion. The second infusion of ATG/placebo given over a minimum of 6 hours and maximum of 10 hours. The infusion can be slowed or temporarily stopped to treat signs or symptoms of cytokine release with a maximum infusion time for each infusion of 10 hours.
Visits 1.1-1.3*	PK samples should be drawn on target days 2 and 4. Window for day 7 PK draw is ± 1 day.
Visit 2:	± 3 days

Visits 3:	± 7 days
Visits 4 to 13:	± 14 days

*subset of participants, as detailed in section 5.2.1.

5.5.1 Visit Window for Participants who Progress to Stage 3

Once a participant has reached primary endpoint (Stage 3 T1D), the participant will continue study visits according to Appendix 2. The initial study visit is to take place within 12 weeks from date of diagnosis. Study visits will then be completed every six months and within ± 14 days from the target date. The target date will be calculated from the date of the participant's initial visit post diagnosis of stage 3 T1D (1st MMTT visit). Participants who develop diabetes will be followed for a minimum of 1 year. Once follow-up within this study has finished, participants have the option to be followed in TrialNet's LIFT protocol for monitoring or other studies that are available.

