APPENDIX 2 - Schedule of Assessments for Participants Who Progress to Stage 3 T1D

	Initial ¹				
Month		6	12	18	24+ ⁶
Visit Window	+/- 7 days	+/- 14 days	+/- 14 days	+/- 14 days	+/- 14 days
Directed Physical Exam	X	X	X	X	X
Intensive Diabetes Management Review	X	X	X	X	X
MMTT ²	X	X	X	X	X
HbA1c ²	X	X	X	X	X
Concomitant Medication	X	X	X	X	X
Adverse Event Assessment	X	X	X	X	X
Urine Pregnancy Test	X	X	X	X	X
Mechanistic Assessments ³	X	X	X	X	X
Unblinded CGM Wear ⁴	X	X	X	X	X
Fecal Sample ⁵					

1. Initial Visit: To occur within 12 weeks from date of diagnosis of Stage 3 T1D
2. MMTT to be performed only when residual C-Peptide is evident at last available MMTT result. If c-peptide is no longer detectable at last available MMTT result, the participant will no longer complete MMTTs. From this point, the participant will only complete the other visit assessments, including HbA1c, which can be done in-person or remotely. Some individuals with c-peptide may decline undergoing MMTT visits but still wish to participate in the study. In this case visit assessments may be obtained in person or remotely.
3. Samples may be obtained for mechanistic studies developed to address the aims of this protocol, including RNA, plasma, serum, DNA, and/or measures of immune cell number and function. At no time will blood volume exceed what is allowable per the participant's age and body weight (5 mL/kg per day and 9.5 mL/kg over an 8-week period for children under age 18).
4. Unblinded CGM wear for 7-10 days will occur after each visit in the Stage 3 T1D schedule.
5. If participant is diagnosed with Stage 3 T1D <1 year after baseline (V0), fecal sample can be collected at a stage 3 visit if the visit occurs 3 months \pm 7 days and/or 12 months \pm 14 days after baseline (window based on the Stage 2 schedule for V3 and V5).
6. The bi-annual schedule will continue as long as follow-up continues within the scope of this trial.

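### The Visit 0 stool sample may be collected up to 3 days after infusion 1, so a sample inside the baseline window can be post-treatment

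*Combined protocol and SAP*

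**What the plan says.** The fecal-sample row of Appendix 1 is marked at Visit 0, month 3 and month 12. Its note sets the timing: "Willing participants will collect fecal samples within +/-3 days of the indicated visit at home". Participants may "either bring to the research visit or ship samples back to the site", so a sample collected after the visit has an allowed route back. The note adds: "Participants who agree to collect samples should be encouraged to provide samples at all 3 timepoints". It gives no separate rule for Visit 0 and does not mention the infusion or the premedication.

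Visit 0 is the baseline. Appendix 2, note 5, says so in passing: "If participant is diagnosed with Stage 3 T1D <1 year after baseline (V0), fecal sample can be collected at a stage 3 visit". It is also the first dosing day. Section 4.1: "Infusion 1 (visit 0) will be ATG/Placebo at 0.5 mg/kg IV over a minimum of 6 hours". For infusion 2, section 5.5 says: "The second dose should be given no earlier than 12 hours and no later than 30 hours from the start of the first infusion".

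Steroid exposure differs by arm. Section 4.5 states that "methylprednisolone 0.25 mg/kg IV will be given no less than 30 minutes before each infusion of active drug", while the placebo group receives saline. Under section 4.4.2, hydrocortisone goes into the ATG bag for peripheral administration and not into the placebo bag.

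Section 5.3 gives the purpose of the stool collection: to "explore whether the gut microbiome can predict response to therapy and whether therapy induces changes in the microbiome".

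**The concern.** A baseline value should be measured before treatment starts. Under the note, a sample collected after infusion 1, or after both infusions, is still within the window and still belongs to Visit 0.

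The consequence differs by arm. A late sample in the placebo arm follows neither ATG nor steroid. A late sample in the ATG arm follows both. Randomization does not remove that difference, because it arises from the treatment itself.

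Two uses are at stake. If the Visit 0 sample serves as a predictor of response, a post-dose value may already reflect the treatment whose effect it is meant to predict. If it serves as the reference for change, any early shift caused by ATG or steroid enters the reference value in the ATG arm only, and the change from baseline is distorted in that arm.

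**Working it through.** There is no stated figure to reproduce. The check is time arithmetic from the protocol's own limits, with the start of infusion 1 as 0 h.

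**Inputs**
- Stool window: 3 days either side of the visit (Appendix 1, fecal-sample note), that is about -72 h to +72 h, 144 h in total.
- Infusion 2 starts 12 to 30 h after the start of infusion 1 (sections 4.1, 4.4.2 and 5.5).
- Each infusion lasts 6 to 10 h (sections 4.1 and 4.4.2).
- Methylprednisolone is given at least 30 minutes before each infusion, ATG arm only (section 4.5).
- Hydrocortisone is in the ATG bag only, for peripheral administration (section 4.4.2).

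**End of infusion 2**
- Earliest: 12 + 6 = 18 h.
- Latest: 30 + 10 = 40 h.

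**Share of the permitted window**
- After the start of infusion 1: 72 / 144 = 50%.
- After the end of infusion 2, latest case: 72 - 40 = 32 h, and 32 / 144 = 22%.
- After the end of infusion 2, earliest case: 72 - 18 = 54 h, and 54 / 144 = 37.5%.

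These are shares of permitted time, not of samples.

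**Exposure before the stool sample, infusions on schedule**

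| Collection time | ATG arm | Placebo arm |
|---|---|---|
| Before premedication for infusion 1 | none | none |
| About 24 h (day +1) | one or both ATG infusions begun, one or two methylprednisolone doses, hydrocortisone if peripheral | no ATG, no steroid |
| 48 to 72 h (days +2 and +3) | both ATG infusions, two methylprednisolone doses, hydrocortisone if peripheral | no ATG, no steroid |

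The day +1 row is mixed because 24 h lies inside the 12 to 30 h range for the start of infusion 2. By 48 h both infusions are over, since 40 h is the latest end.

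**Comparison with other notes in Appendix 1.** The first CBC, the first PK sample and the first anti-drug-antibody sample are each tied explicitly to the time before infusion 1. The fecal-sample note has no such words, and section 5.3 gives no timing that would supply them.

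**What cannot be computed.** The bias would require the distribution of actual collection times and the size of any shift in the microbiome within 72 h of dosing. The documents give neither.

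**The case against.** The case for leaving the note alone has some substance. Stool is collected at home, while CBC, PK and antibody samples are clinic blood draws that staff can time, so a symmetric window is an understandable concession to feasibility. The mechanistic-assessments note, also marked at Visit 0, likewise has no pre-infusion rule. Bringing the sample to the visit is the first return route named and points to collection before or at the visit, so late samples may be few. Late samples could also be dropped at analysis if collection dates are kept, although the fecal-sample note does not say that they are. The manual of operations is not among the documents and might narrow the window. All this limits how often the problem arises. None of it changes what the protocol permits.

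Three stronger readings are tempting, and the documents do not support them.

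- A reader might infer that every sample from day +1 to day +3 in the ATG arm follows two methylprednisolone doses and hydrocortisone. A day +1 sample may follow only one dose, and hydrocortisone is added only for peripheral administration.
- A reader might count calendar days, find that 3 of 7 (43%) fall after the infusion day, and infer that the ATG change from baseline is attenuated in proportion. That assumes collection spread evenly over the window, and an early shift of known size in the same direction as the later one. A transient or opposite early shift need not attenuate the change and could inflate it.
- A reader might infer that the question of whether therapy changes the microbiome is compromised as a whole. Section 5.3 states an exploratory aim and names no reference value or change score. A comparison of the randomized arms at months 3 and 12 that does not use the Visit 0 sample is unaffected.

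**Conclusion.** The point holds as a defect of timing. The stated rule lets a stool sample taken after one or both infusions count as baseline, with ATG and steroid exposure in one arm only. It compromises the exploratory use of baseline microbiome as a predictor of response, and any analysis of change from baseline. Up to half of the permitted window lies after the start of infusion 1, and 22% to 37.5% lies after the end of infusion 2, if both infusions are given on schedule. The resulting bias has no derivable size or direction.

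The importance is low. Collection is voluntary and exploratory. The primary outcome, the secondary analyses listed in section 8.2, the sample size and the type I error do not depend on it. It is still worth correcting because a pre-treatment sample cannot be obtained once dosing has begun. The conclusion rests on the protocol text alone; a stricter rule in the manual of operations would remove the problem in practice but not in the protocol.

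**What to change.** Amend the fecal-sample note in Appendix 1:

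- Keep the window of 3 days either side for months 3 and 12.
- Require the Visit 0 stool sample before infusion 1 and its premedication, for example from day -3 to pre-dose on day 0.
- Record the date and time of collection.
- Label any later Visit 0 sample as post-dose and exclude it from baseline.

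This takes a sentence or two in one note and changes no visit, dose or clinical rule. Consent is obtained at the screening visit, so kits can be handed out in time. The downside is that some late samples, in an already optional collection, will not be usable as baseline. How many is unknown, and it should fall once participants are told to collect before the visit.
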